Study Objectives	
The primary objective is to evaluate the effectiveness of a post inpatient discharge virtual psychiatric care team compared to standard care, to reduce 30-day all cause non-elective acute care utilization (ED, observation, and inpatient encounters).
 
Secondary objectives of the evaluation include:
 
 • Compare the effectiveness of the VPTC program compared to standard care, on 60-day all cause non-elective acute care utilization (ED visits, observation, and inpatient encounters). • Compare the effectiveness of the VPTC program compared to standard care, on 30-day behavioral health acute care utilization (ED visits, observation, and inpatient encounters). • Examine the percent of patients that had a behavioral health office visit within 7 days of discharge to standard of care • Examine the count of all cause avoidable ED visits within 30 days of discharge 
Exploratory analyses:
 
 • Count of patients: Identified, Refused, Enrolled, Graduated, Did not graduate and reason • Characterize: demographics and Charlson comorbidity score • Assess symptom improvement 
 ○ Suicidal ideation: 
 ▪ Percent of patients with a PHQ-9, Question 9=0 upon graduation among patients with an initial Q9>0 ○ Depression reduction: 
 ▪ Percent of patients with a 5 point reduction of their PHQ-9 score who had an initial PHQ-9 score ≥ 10 ▪ Show the distribution of PHQ-9 score reduction among participants ○ Depression remission: Percent of patients with a PHQ-9 score <5 upon graduation who had an initial PHQ-9 score ≥ 5
Inclusion Criteria	
Inclusion criteria:
 
 • Residency or shelter in North Carolina • 18 years of age or older on the day of discharge

	
• Access virtual care (phone/video)• Discharged from a behavioral health hospital or a behavioral health unit 
Exclusion criteria: None

Study Procedures	
The VPTC program has a focus on removing obstacles and social determinants that often impede patients from engaging in post hospitalization care. This program would support vulnerable patients, engaging them in virtual services to assist their transition to appropriate and patient centered outpatient care.
 
This study is comprised of a pilot and a pragmatic trial.
 
For the pilot, the Center for Outcomes Research and Evaluation (CORE) team will lead a qualitative evaluation of the psychiatric virtual transition of care (VPTC) program's implementation. The study team will gather first-hand accounts from patients and clinicians regarding their program experiences and program utilization. Changes to the program can be made as needed to optimize enrollment and implementation. The qualitative evaluation will assess the strengths and weaknesses of the VPTC program so modifications can be implemented. The pilot location will not be a part of the trial.
 
For the trial, the VPTC program will be compared to standard care through a cluster randomized by site, stepped-wedge design. Behavioral Health facility or units that have discharged patients meeting inclusion criteria will be randomly assigned as either an intervention or standard care site. Intervention sites will be those using the VPTC program. This evaluation design will integrate into current workflows for the measurement of outcomes. Prior to discharge, patients may be referred to the VPTC program if they report residency or shelter in North Carolina, are 18 years of age or older on the day of discharge and can access virtual care (phone/video).
 
The VPTC program is defined by several key components:
 
• Introduction to the patient follow-up process• Psychiatric consultation• Medication management services with pharmacological consultation• following of Health Coaching participation (Movement, Nutrition, Sleep Hygiene, Stress Management, Pain Management, Perinatal/Postpartum Mood Disorders, Substance abuse) and provide treatment recommendations• Tracking of behavioral health symptoms (Depression, Anxiety, Suicidal ideation) and provide treatment recommendations• Health coaching; Psychoeducational support• Treatment and safety planning• Appointment reminders• Coordination for financial assistance• Assistance connecting with an outpatient care provider• Placement into an appropriate case management program, if needed

	
• Navigation to additional psychiatric or substance use services, if needed• Motivational interviewing and brief therapeutic recommendations, if needed
Statistical Analysis	Analyses will include all patients identified as having been discharged and meeting the inclusion criteria. Baseline comparisons of the intervention and usual care groups will be made using univariate analyses. The primary analysis will be conducted using generalized linear mixed models with fixed effects for intervention, and intervention multiply by the time, accounting for the cluster randomized trial design with a random cluster (hospitals) or time (steps) effect. Results will be presented with odds ratios and 95% confidence intervals.

LIST OF ABBREVIATIONS

BHI	Behavioral Health Integration
CORE	Center for Outcomes Research and Evaluation
C-SSRS	Columbia – Suicide Severity Rating Scale
EDW	Enterprise Data Warehouse
VPTC	Virtual Psychiatric Transition of Care
NC	North Carolina
PHI	Private Health Information
PHQ-2	Patient Health Questionnaire - Screener for Depressive Disorders
PHQ-9	Patient Health Questionnaire – Screener for Severity of Depression
SOP	Standard Operating Procedures

TABLE OF CONTENTS

1.1.	Hypothesis.....	8
1.2.	Primary Objective	8
1.3.	Secondary Objectives	8
1.4.	Exploratory Analyses	8
2.	BACKGROUND	9
3.	RATIONALE	9
4.	SUBJECT AND SITE SELECTION	10
4.1.	Accrual.....	10
4.2.	Accrual – Subjects	10
4.3.	Participating sites	10
4.4.	Inclusion\Exclusion Criteria	11
4.4.1.	Inclusion Criteria	11
4.4.2.	Exclusion Criteria	11
4.5.	Evaluable Population	11
5.	OVERALL DESIGN.....	11
5.1.	Variables	11
5.1.1.	Primary Outcome Variable.....	11
5.1.2.	Secondary Outcome Variables	11
5.1.3.	Exploratory Variables	12
5.2.	Trial Design	12
5.2.1.	Justification for stepped wedge cluster randomized control trial	12
5.2.2.	Virtual Psychiatric Transition of Care Program	13
5.2.2.1.	Zero Suicide Pathway	13
5.2.2.2.	VPTC Pathway	13
5.3.	Patient Graduation from the VPTC Program	14
5.4.	Continuation of the Intervention	14
6.	QUALITATIVE REVIEW	14
7.	DATA COLLECTION AND REPORTING.....	15
7.1.	Sample Size Analysis	16
7.2.	Statistical analysis	16
7.3.	Missing Data	17
7.4.	Training	17
7.5.	Data Collection Dates.....	17

8. INTERVENTION PLAN.....	18
8.1. Behavioral Health Professional Assessments.....	18
8.2. Follow-up Assessments.....	18
8.3. Psychiatric Virtual Appointments.....	18
9. STUDY GOVERNANCE	19
10. SAFETY RISKS AND REPORTING.....	19

1.1. Hypothesis

Patients discharged from behavioral health hospitals or units that offer a virtual psychiatric transition of care (VPTC) program will have a lower 30-day all cause acute care utilization rate (ED, observation, or inpatient) compared to patients discharged from behavioral health hospitals or units that do not offer the VPTC program.

1.2. Primary Objective

The primary objective is to evaluate the effectiveness of a virtual psychiatric care team compared to standard care, to reduce 30-day all cause non-elective acute care utilization (ED, observation, and inpatient encounters).

1.3. Secondary Objectives

- Compare the effectiveness of the VPTC program compared to standard care, on 60-day all cause non-elective acute care utilization (ED, observation, and inpatient encounters).
- Compare the effectiveness of the VPTC program compared to standard care, on 30-day behavioral health acute care utilization (ED, observation, and inpatient encounters).
 - Behavioral health: ED visit with a telepsychiatric consult; inpatient or observation discharge from a behavioral health hospital or unit)
- Examine the percent of patients that had a behavioral health office visit within 7 days of discharge
- Examine the count of avoidable ED visits within 30 days of discharge

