5. OVERALL DESIGN

5.1. Variables

5.1.1. Primary Outcome Variable

The primary outcome variable is 30-day all cause non-elective acute care post discharge utilization (ED, inpatient, and observation encounters).

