5.1.2. Secondary Outcome Variables

- a. Demographic characteristics (age, race, gender, insurance plan)
- b. Charlson comorbidity index score
- c. 60-day all cause non-elective acute care utilization (ED visits, observation, and inpatient encounters).
- d. 30-day behavioral health acute care utilization (ED visits, observation, and inpatient encounters).
- e. A behavioral health office visit within 7 days of discharge
- f. An avoidable ED visit within 30 days of discharge

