5.2.2.2. VPTC Pathway

If a patient has not attempted suicide as the reason for admission, VPTC clinicians will begin outreach with the patient within the first 24-72 hours after discharge. The first outreach with the patient will be completed by a licensed clinician who will complete a brief psychosocial assessment with the patient. After the initial outreach is completed a health coach will then reach out to the patient to set a weekly schedule. The weekly outreach with the VPTC health coach will be patient centered and patient specific. These outreach will help support patients through goal setting/treatment plans, medication support, linkage and support to community resources, and safety planning. These outreach will also help patients identify any barriers they may have in attending their follow up care with their outpatient community providers. Throughout the outreach at any point and time if a patient has a question or concern about their medication the VPTC licensed practicing nurse can contact the patient to help address those needs. At each outreach patient's safety is also assessed. At any point in the outreach if a patient endorses any safety concerns that patient will be assessed by a licensed qualified clinician to identify those safety concerns and create a safety plan with the patient.

If the patient is scheduled with a VPTC psychiatric provider for a hospital follow-up appointment, an LPN (Licensed Practical Nurse) will outreach to the patient before that visit to complete the nursing intake. The patient will then have their hospital follow up visit either with their community provider, or the VPTC psychiatric provider. The VPTC psychiatric provider will review medications that the patient started on the inpatient unit or emergency department and provide any further education, adjustments, and support. The provider is able to order the medications. The VPTC program will also have support from a psychiatric provider through weekly treatment team huddles to help support patients and identify any barriers they may be facing.

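### The 30-day behavioral health utilization outcome is defined by consult and unit rather than by reason for the encounter, and it lacks the non-elective limit that the primary and 60-day outcomes carry

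*Combined protocol and SAP*

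**What the plan says.** The outcome appears in three places: the synopsis, section 1.3 (Secondary Objectives) and section 5.1.2 (Secondary Outcome Variables). Section 5.1.2 lists it as "30-day behavioral health acute care utilization (ED visits, observation, and inpatient encounters", with no definition, and the synopsis is equally bare. Only section 1.3 says what makes an encounter behavioral: "Behavioral health: ED visit with a telepsychiatric consult; inpatient or observation discharge from a behavioral health hospital or unit".

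The neighbouring outcomes are limited in a way this one is not. The 60-day outcome in section 1.3 is "60-day all cause non-elective acute care utilization (ED, observation, and inpatient encounters". For the primary outcome, section 5.1.1 states: "The primary outcome variable is 30-day all cause non-elective acute care post discharge utilization (ED, inpatient, and observation encounters". The behavioral health outcome in section 1.3 is simply "30-day behavioral health acute care utilization (ED, observation, and inpatient encounters".

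Section 7 draws utilization from the electronic medical record and billing systems. Section 7.2 applies the primary outcome's analysis plan to the secondary outcomes as well.

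**The concern.** This is the acute-care outcome specific to behavioral health, in a programme that section 2 says is meant to reduce suicide risk. The definition raises three difficulties.

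- **ED visits.** The consult is something done to the patient after arrival. Two visits for the same crisis are classified differently if one had a telepsychiatric consult and the other did not.
- **Stays.** A stay is behavioral only if the discharge is from a behavioral health hospital or unit. Self-harm treated on a medical unit falls outside it.
- **Elective use.** Without a non-elective limit, a planned behavioral health admission is a failure here but not in the primary outcome.

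The first difficulty matters most for inference. A process-based outcome moves when the process moves. If consults became rarer or more common over the trial, a reader could not tell fewer crises from fewer consults. The second is a coverage gap in both periods. The third could make this outcome disagree with the primary for a reason of wording alone.

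**Working it through.** The plan gives no event rate, consult share, effect size or power for this outcome, so there is no stated figure to reproduce. The check compares the text first, then gives an illustration on assumed inputs.

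**Text, side by side**

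- Primary outcome (1.2, 5.1.1): all cause, non-elective, any unit, no consult condition.
- 60-day outcome (1.3, 5.1.2): the same limits over a longer window.
- 30-day behavioral health outcome (synopsis, 1.3, 5.1.2): no non-elective limit in any of the three places. The consult and unit conditions appear in 1.3 only.
- Not stated anywhere: who orders telepsychiatric consults, how often they occur, whether every ED has them in every period, and whether an ED visit that ends in a medical-unit admission still counts as an ED visit. If it does, a medical-unit self-harm stay is captured whenever that ED visit had a consult.

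**How far a change in consult use would move the outcome**

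Let c be the proportion of patients whose only behavioral health encounter within 30 days is an ED visit, equal in both periods. Let q0 and q1 be the shares of those visits with a consult in control and intervention periods. Then:

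shift in measured rate = c × (q1 − q0)

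Assumptions, none from the documents: c = 6% (range 4% to 8%), and consult shares as given below. With q1 = q0 the shift is zero, and its sign follows the change in consult use.

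*Route A, through the programme.* Section 7.1 expects 40% enrolment, and a programme effect on consults would act through patients who enrol. If the share falls 20 points among enrollees only:

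- c = 6%: 0.06 × 0.4 × 0.20 = 0.48 points
- c = 4%: 0.04 × 0.4 × 0.20 = 0.32 points
- c = 8%: 0.08 × 0.4 × 0.20 = 0.64 points

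A 10-point fall among enrollees halves these to 0.24 (0.16 to 0.32). A 20-point fall across the whole arm would give 0.06 × 0.20 = 1.2 points, but it needs a fall of 0.20 / 0.40 = 50 points among enrollees.

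*Route B, calendar drift, with no programme effect on consults.* In the example schedule in section 5.2.1, location k has control periods 1 to k, with mean (k + 1)/2, and intervention periods k + 1 to 8, with mean (k + 9)/2. The gap is (k + 9)/2 − (k + 1)/2 = 4 periods, or 12 months, for every location. If the consult share drifts linearly by 20 points from period 1 to period 8 (seven steps), the unadjusted within-location shift is:

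- c = 6%: 0.06 × 20 × 4/7 = 0.7 points
- c = 4%: 0.5 points
- c = 8%: 0.9 points

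Section 7.2 plans within-location comparisons without adjustment for time. Its main model names fixed effects for intervention and for intervention by time, with a random effect for location or for step, so removal of drift is not assured there either.

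**The case against.** The strongest reply is that nothing in the plan connects the programme to consult use. A reader might infer that having a VPTC psychiatric provider makes ED staff less likely to call for a consult, so that the programme improves this outcome artificially. The documents do not support that. The closest text, "The VPTC psychiatric provider will review medications that the patient started on the inpatient unit or emergency department", concerns medication review after discharge. Nor can safety plans be treated as exclusive to intervention periods: section 3 dates the Zero Suicide pathway to 2019, and section 10 refers to similar virtual programmes for patients discharged from the emergency room. This part of the objection stands in full.

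A reader might also infer that the programme generates planned admissions and so harms itself on this outcome. The synopsis lists "Navigation to additional psychiatric or substance use services, if needed", and section 5.3 lists transition to a psychiatry or treatment program and, separately, inpatient readmission. None of these describes a planned admission. The missing limit may be a drafting slip, since section 1.1 also omits it for the primary outcome: "lower 30-day all cause acute care utilization rate (ED, observation, or inpatient". That explains the omission but does not settle it. All three statements of this outcome lack the limit, and an analyst following them would count elective stays.

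The medical-unit gap applies in both periods, so it limits coverage and is not a demonstrated bias. The all-cause outcomes also count ED visits without a consult and non-elective medical-unit stays. Both points stand and confine the matter to one secondary outcome.

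Finally, diagnosis coding in the ED is imperfect, so replacing the current definition outright would trade one error for another. That is a reason to add a diagnosis-based analysis, not to substitute it.

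**Conclusion.** The concern holds as a weakness of definition in one secondary outcome. It is certain from the text that a behavioral health event is set by consult and unit, that some psychiatric ED visits and medical-unit self-harm stays can be missed, and that the non-elective limit is absent in all three places.

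It is conditional that any difference in consult use between control and intervention periods would move the outcome without a change in crises. The documents do not show such a difference. The illustrated shifts, 0.16 to 0.64 points by a route through enrollees and 0.5 to 0.9 points by calendar drift, rest wholly on assumed ED-visit rates and consult shares, and they reverse if consult use rises. They should not be read as estimates of bias. The 2.4-point difference in section 7.1 belongs to the all-cause primary outcome and is no benchmark for this one.

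The primary and 60-day results are unaffected. This is a cheap improvement to make before analysis.

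**What to change.** 1. Add the non-elective limit to this outcome in the synopsis, section 1.3 and section 5.1.2.
2. Keep the consult-and-unit definition, and pre-specify one supporting analysis. It counts any non-elective ED, observation or inpatient encounter in the health system's own record and billing data, starting within 30 days of index discharge, with a principal mental health, substance-use or self-harm diagnosis, whatever the consult or unit. It should not claim to cover outside facilities, because section 7 describes no outside claims data.
3. Report the telepsychiatric consult rate among diagnosis-defined ED visits, by period and arm, so that readers can see whether consult use changed.

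The cost is a wording change, one diagnosis code list and a little extra analysis of data already being retrieved. The drawback is imperfect ED diagnosis coding, which is why the diagnosis-based version is offered as support and not as a replacement.

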1.4. Exploratory Analyses

- Qualitative review of the program
- Count of patients: Identified, Refused, Enrolled, Graduated, Did not graduate and reason
- Characterize: demographics and Charlson comorbidity score
- Assess symptom improvement
 - Suicidal ideation:
 - Percent of patients with a PHQ-9, Question 2=0 upon graduation among patients with an initial Q2>0
 - Depression reduction:
 - Percent of patients with a 5 point reduction of their PHQ-9 score who had an initial PHQ-9 score ≥ 10
 - Show the distribution of PHQ-9 score reduction among participants
 - Depression remission: Percent of patients with a PHQ-9 score <5 upon graduation who had an initial PHQ-9 score ≥ 5

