5.1.3. Exploratory Variables

- g. Assess symptom improvement for depression
 - i. Initial- PHQ-9 total score
 - ii. Post- PHQ-9 total score
- h. Assess suicidal ideation
 - i. Initial- PHQ-9, Q9 score
 - ii. Post- PHQ-9, Q9 score

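### Section 1.4 defines the suicidal-ideation outcome on PHQ-9 Question 2, while the synopsis and Section 5.1.3 use Question 9

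*Combined protocol and SAP*

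**What the plan says.** Three places in the current text define how suicidal ideation will be measured as an outcome.

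- **Section 1.4 (Exploratory Analyses)**, under symptom improvement: "Percent of patients with a PHQ-9, Question 2=0 upon graduation among patients with an initial Q2>0".
- **Synopsis, Study Objectives**, under the same suicidal-ideation label: "Percent of patients with a PHQ-9, Question 9=0 upon graduation among patients with an initial Q9>0".
- **Section 5.1.3 (Exploratory Variables)**: under "Assess suicidal ideation" two variables are listed, "Initial- PHQ-9, Q9 score" and "Post- PHQ-9, Q9 score". The only other PHQ-9 variables there are the initial and post total scores.

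The text contains no amendment log and no remark that would make one of these definitions superseded.

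**The concern.** One outcome has two definitions that use different questionnaire items. In Section 1.4 the item number appears twice, once in the success criterion and once in the denominator condition, and it is Question 2 both times. The sentence is therefore consistent within itself, and a programmer working from the objectives section could code it without seeing a problem.

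The stakes come from what the outcome stands for. Section 2 gives lowering suicide risk as one aim of the program, and Section 5.2.2.1 sets up a dedicated pathway for patients who have attempted suicide. The Columbia scale is administered at initial and follow-up contacts (Sections 8.1 and 8.2), but no objective or outcome variable uses it. The PHQ-9 item is therefore the only listed outcome that captures change in suicidal ideation. Section 11 promises a final report of all findings to stakeholders, so a figure built on the wrong item could circulate under that label.

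**Working it through.** The plan states no figure on this point and no formula from it needs reproducing. The check is a comparison of the three definitions.

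| Place | Denominator | Success |
|---|---|---|
| Synopsis | initial Q9 > 0 | Q9 = 0 at graduation |
| Section 1.4 | initial Q2 > 0 | Q2 = 0 at graduation |
| Section 5.1.3 | initial Q9 score (variable only) | post Q9 score (variable only) |

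**Step 1: is anything else different?** No. The other symptom bullets agree between the synopsis and Section 1.4: a 5-point reduction among patients starting at 10 or more, and a score below 5 among patients starting at 5 or more. Only the item number in the suicidal-ideation bullet differs.

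**Step 2: do the two definitions give different results?** Written out, they are

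- P9 = n(initial Q9 > 0 and final Q9 = 0) / n(initial Q9 > 0)
- P2 = n(initial Q2 > 0 and final Q2 = 0) / n(initial Q2 > 0)

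A patient who starts with Q2 > 0 and Q9 = 0 enters P2 but not P9. A patient who starts with both items positive and ends with Q2 = 0 and Q9 > 0 is a success in P2 and a failure in P9. Numerator and denominator both change, and the shift may go in either direction.

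**Step 3: which version is the error?** The documents do not print the item wording, so this has to rest on their own usage. Two of the three places tie suicidal ideation to Question 9. Section 5.1.3 lists no Question 2 variable, and Question 2 cannot in general be recovered from what it does list, because the total minus Q9 gives only the sum of all the other items. The Section 1.4 outcome therefore cannot be built from the listed variables, whereas the synopsis outcome can.

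**Step 4: could the 2 refer to the PHQ-2?** The abbreviation list includes the PHQ-2, but Section 1.4 names the PHQ-9 explicitly, and the list describes the PHQ-2 as a screener for depressive disorders. That reading does not rescue the sentence.

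**Step 5: how large is the effect?** It cannot be computed. It depends on the joint distribution of the two items at the start and at graduation, and the documents give none of it.

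**The case against.** The best case on the other side is that this is a transcription slip with little consequence. The outcome is one descriptive percentage among the exploratory analyses. Section 7.2 extends the analysis plan to secondary outcomes only, so no test or model is attached to it. It is defined at graduation and so covers only patients enrolled in the program; it does not compare the arms, and no conclusion about effectiveness can depend on it. The variable list and the synopsis already point to Question 9, so a careful analyst would probably settle on it. Assessment of suicidality in patients is unaffected, since the Columbia scale is used at the contacts whatever Section 1.4 says.

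Most of this stands, and it limits the weight of the point. It also weakens any worry that two definitions invite a choice after the data are seen: choosing Question 2 would mean departing from both the synopsis and the variable list, and there is no error rate to inflate. What does not follow is that the text can stay. Section 1.4 is an outcome definition in the body of the protocol, it is contradicted elsewhere, and a reader who has only that section has no signal that it is wrong.

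**Conclusion.** The concern holds. Section 1.4 names a different PHQ-9 item from the synopsis and Section 5.1.3 for the same labelled outcome, in both the numerator and the denominator condition. Coding it as written would report the wrong item in the wrong subset of patients.

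The numerical size is unknown. The scope is one exploratory percentage; the primary and secondary outcomes, the sample size, the power and the type I error are not affected. The conclusion that Question 9 is the intended item assumes that the synopsis and the variable list express the intent. That is the only reading under which all three places agree without adding a variable. The correction should be made, but the validity of the trial does not depend on it.

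**What to change.** In Section 1.4, change the item from Question 2 to Question 9 in both the success criterion and the denominator condition, so that the bullet matches the synopsis and Section 5.1.3. Confirm that any data extract or analysis code already written for this outcome reads the Question 9 score at both time points.

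The cost is a one-line protocol correction and a short code check. No additional data are needed beyond the variables already listed, and neither the design nor the conduct of the trial changes.
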